9.2.2 Study observation period

The first interim report will be submitted to the European Medicines Agency (EMA) at year 4 following the start of data collection, and then will be submitted on a biennial basis (i.e., five interim reports in total for the entire study period). Each patient selected will be followed from his/her respective index date until the earliest occurrence of:

[figure not shown]
- Loss to follow-up (i.e., patient no longer covered in the data source)
- Death (NOTE: The approach for evaluation of death outside of a hospital setting will differ by database)
- End of study follow-up period (10 years after the last patient selected per database)

The cohorts are considered to have dynamic inclusion periods. At each interim analysis, the cohort populations and patient matching will be redefined. Patients in the reference cohort who have switched from any other MG treatment to efgartigimod will be considered as having

³ Only new users of efgartigimod will be included in the efgartigimod cohort, that is, patient who receives a first prescription, or dispensing, or has a procedure code for efgartigimod during the study period, and without a prescription or dispensing or a procedure code for efgartigimod in the previous 12 months.

reached the end of their follow-up period at the time of the switch and will thus be censored from the reference group but counted in the efgartigimod group.

Figure 1. Study observational period

9.2.2.1 Switch from reference cohort to efgartigimod cohort or multiple cumulative exposure to efgartigimod during study period

It is anticipated that during the study period, patients who are in the reference cohort at study entry may initiate efgartigimod at a later time; or patients who are in the efgartigimod cohort at study entry may reinstate efgartigimod a long time following their index exposure.

Details on handling patients who switch therapies or with multiple cumulative exposure to efgartigimod is briefly described in section 13 Data analysis and will be elaborated in the SAP.

9.3 Variables

Variables that will be evaluated to determine subpopulations of interest include patient demographics and exposure to non-steroid immunosuppressants.

Risk factors for malignancy will be evaluated as potential covariates for study analysis.

Exposure to MG therapies will be captured:

- Efgartigimod

- Non-efgartigimod maintenance therapies, including:
 - Acetylcholinesterase (AChE) inhibitors
 - Corticosteroids
 - Non-steroidal immunosuppressants
 - Monoclonal antibodies

The following variables will be collected to assess the impact of healthcare resource utilization:

- Hospitalisations
- MG-related hospitalisations
- ER visits
- MG exacerbations, when available in the database
- MG crises

These variables will also be collected during the look-back period if possible.

9.4 Efgartigimod exposure definition and measurements

Efgartigimod is administered in cycles of 4 weekly administrations followed by an efgartigimod-free period. The initiation of the next cycle is based on clinical need.

This schedule of administration is based on results of clinical trials that showed that clinical response is following or even exceeding the duration of IgG reduction. Majority of patients receive 5-7 cycles per year which has been confirmed in real world studies ([Bhavaraju-Sanka 2024](#)).

In this study, a patient will be considered an efgartigimod exposed patient if he/she has received at least one (1) dose of efgartigimod. Exposure to efgartigimod IV and SC starts with the initial exposure date for the medication found in the patient record (patient's index date). It is determined that consecutive doses administered greater than 21 days apart will be considered a different cycle.

Based on these elements, the following treatment patterns will be identified:

- Ever used: patients who receive 1 administration to up to 1 cycle (ie., max. of 4 once weekly administration with less than 21 days between).
- Infrequent use: patients who have a *Medication Possession Ratio* (MPR) < 60%. MPR is defined as the sum of drug supply days covered by each cycle (28+21= 49 days) divided by the time elapsed between the first supply and the end of the follow-up period.
- Continuous use: patients who have received ≥ 2 subsequent cycles without any interruption of more than 120 days between cycles.
- Intermittent use: patients who have at least one interruption of more than 120 days between two consecutive cycles. If sample size permits, the intermittent group may be stratified according to MPR subclasses.

- Discontinuation is defined as a gap period of at least 120 days after the last claim/prescription/dispensing.

Additionally, taking into account the variable follow-up time and time interval between cycles, the following will be measured for efgartigimod:

- Number of administrations per year
- Total duration of the exposure
- Total number of administrations

The coding algorithms to identify efgartigimod exposure vary across different databases. In the US database (i.e., Optum), the coding algorithm will consist of relevant National Drug Code (NDC) and/or Healthcare Common Procedure Coding System (HCPCS) Level II procedure codes. In Europe, relevant anatomical therapeutical chemical (ATC) codes will be used to identify efgartigimod. UK CPRD uses a different medication coding system. The details of product codes associated with efgartigimod in selected databases will be provided in the SAP.

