Note: the malignancy categories will include thymic and non-thymic (all other types); non-thymic will be further categorized into solid tumours by organ and hematopoietic/lymphoid and related

Secondary objectives

In MG patients treated with efgartigimod compared to MG patients on any other MG therapy:

- To evaluate the long-term risk of malignancies overall and by type in MG patients with malignancy history in the lookback period
- To evaluate the long-term risk of malignancies by duration of efgartigimod exposure
- To evaluate the long-term risk of malignancies in subpopulations with increased risk for malignancy:
 - elderly – age 65 years and older
 - chronic use (i.e., ≥ 1 year) of corticosteroids

Exploratory objectives

- To evaluate the long-term risk of malignancies in MG patients treated with other FcRn antagonists
- To assess time to the first occurrence of malignancy overall and by type of malignancy in MG patients treated with efgartigimod and MG patients on any other MG therapy:
- To assess healthcare resource utilization including:
 - The number of hospitalisations (including MG-related)
 - The number of emergency room (ER) visits, and
 - The number of MG exacerbations and MG crises if available.

¹ A lookback period is a period prior to patients' initiation of index medication (cohort entry) to reliably characterise a patient based on relevant malignancy history, as well as other baseline covariates.

9 Research methods

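### Off the described 5 to 7 cycles a year, the 21-day cycle rule with a flat 49-day credit per cycle gives MPR values and use classes that do not follow the amount of dosing

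*Protocol*

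**What the plan says.** Section 9.4 of the protocol builds its treatment patterns in three steps.

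- **Cycle.** The splitting rule is that "consecutive doses administered greater than 21 days apart will be considered a different cycle".
- **MPR.** The numerator is the "sum of drug supply days covered by each cycle (28+21= 49 days" for each), "divided by the time elapsed between the first supply and the end of the follow-up period". The credit carries no minimum or maximum number of doses.
- **Classes.** An MPR below 60% is *infrequent use*. *Continuous use* means "patients who have received ≥ 2 subsequent cycles without any interruption of more than 120 days between cycles". At least one longer interruption makes *intermittent use*. *Ever used* covers "patients who receive 1 administration to up to 1 cycle (ie., max. of 4 once weekly administration with less than 21 days between").

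The same section describes the usual schedule as four weekly doses followed by a free period, with the next cycle given on clinical need and most patients receiving 5 to 7 cycles a year. Section 7 adds that cycle frequency may differ between patients. Section 9.4 also lists three measures apart from the classes: administrations per year, total duration of exposure, and total administrations. A secondary objective in Section 8 is "To evaluate the long-term risk of malignancies by duration of efgartigimod exposure".

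**The concern.** The cycle count is the only input to the MPR numerator, and it depends on gaps between doses, not on the doses. Closely spaced doses merge into one cycle and earn 49 days once. Widely spaced single doses each open a cycle and earn 49 days every time. The credit therefore tracks dosing only when patients keep close to the described schedule.

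Two statements in the section also fail to fit together. The *ever used* class describes a cycle as "max. of 4 once weekly administration with less than 21 days between", while the splitting rule sets no upper limit on doses. A fifth weekly dose is then outside the cycle by one statement and inside it by the other. A gap of exactly 21 days is neither less than 21 nor greater than 21, yet it is a natural value when doses are given on a weekly grid.

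At stake is the meaning of the pattern classes and the MPR, and of any exposure analysis that may later be built on them.

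**Working it through.** **Inputs, all from Section 9.4:** new cycle if the gap exceeds 21 days; 49 days of credit per cycle; *infrequent* if MPR is below 60%; *continuous* if there are at least 2 cycles and no interruption above 120 days.

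**Formula:** MPR = 49 × number of cycles / days from first supply to end of follow-up.

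**The plan's own figure first.** 28 + 21 = 49 reproduces. The described frequency gives 5 × 49/365 = 67.1% to 7 × 49/365 = 94.0%. The free gaps are about 365/5 − 21 = 52 days and 365/7 − 21 = 31 days, all above 21 and below 120, so these patients are *continuous* and not *infrequent*. On its intended pattern the rule works.

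**The splitting rule applied literally to other patterns:**

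| Pattern | Follow-up (days) | Doses | Cycles | MPR | Class |
|---|---|---|---|---|---|
| Weekly | 365 | 53 | 1 | 49/365 = 13.4% | infrequent |
| Weekly | 1,095 | 157 | 1 | 49/1,095 = 4.5% | infrequent |
| Four-dose cycles, start every 42 days | 1,095 | 105 | 1 | 4.5% | infrequent |
| Four-dose cycles, start every 43 days | 1,095 | 103 | 26 | 26 × 49/1,095 = 116.3% | continuous |
| One dose every 60 days | 365 | 7 | 7 | 7 × 49/365 = 94.0% | continuous |
| Two doses 22 days apart, then none | 1,095 | 2 | 2 | 2 × 49/1,095 = 8.9% | continuous and infrequent |

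**Where the jump sits.** Within a four-dose cycle the last dose falls on day 21. A restart on day 42 leaves a gap of 21 days, which does not open a new cycle; a restart on day 43 leaves 22, which does. One day's difference, with almost the same number of doses (105 against 103), moves the MPR from 4.5% to 116.3%. The 42-day threshold corresponds to 365/42 = 8.7 cycles a year.

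**How soon it shows.** A patient with a single cycle falls below 60% once follow-up passes 49/0.6 = 81.7 days. Section 9.1 plans at least 10 years of follow-up, where the single-cycle MPR would be 49/3,650 = 1.3%. Such a patient cannot be *continuous* (one cycle only) and, with more than four doses, is not *ever used*.

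**The sparse end over longer follow-up.** One dose every 60 days for 10 years gives 61 × 49/3,650 = 81.9%, still above the 60% cut.

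**The case against.** The best defence is that a cycle of 157 doses ignores the four-dose description under *ever used*. If a cycle holds at most four doses, the single-cycle result does not follow. This stands in part. That description sits in the definition of one class and is not joined to the splitting rule or to the MPR, so the section gives two answers for a fifth dose. The fault at the dense end is therefore a contradiction, with the misclassification as the outcome of one reading. Similarly, 28 + 21 suggests a full course plus a tail, and *ever used* distinguishes one administration from one cycle, so crediting a lone dose with 49 days is open to dispute. But nothing in the section gives it any other credit.

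It is also fair to say that the described regimen is classed well, that Section 9.2.2.1 leaves details of cumulative exposure to the SAP, and that Section 13 uses neither the MPR nor the classes in any model. These points limit the consequence. They do not remove it, because Section 9.4 states an operative rule that an SAP would inherit.

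A reader might infer that sparse users generally end up as *continuous* alone. The case of two doses 22 days apart does not show this: it also meets *infrequent* at 8.9%, which is an overlap between the classes and a separate matter.

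**Conclusion.** The point holds for dosing that departs from the described 5 to 7 four-dose cycles a year. There, the literal rule gives 4.5% and *infrequent* to uninterrupted dosing over 3 years, 116% to cycles restarted every 43 days, and 94% and *continuous* to isolated doses every 60 days over one year. The dense-end result assumes that the 21-day rule governs over the four-dose wording; the sparse-end result assumes that a lone dose counts as a cycle. The contradiction over a fifth dose and the unassigned 21-day gap need no assumption.

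A reader might go further and conclude that the duration analysis will show a flattened or reversed exposure-response. The documents do not support that. No section ties these classes to the duration objective, total duration and administration counts are measured separately, and the primary incidence rate ratio in Section 13.2 does not use them. Nor do the documents say how many patients are dosed densely or in isolated doses. If one assumed that 10% to 30% of the *infrequent* class were dense users with a true ratio of 2 and the rest had 1, the class would show 1 + 0.1 = 1.1 to 1 + 0.3 = 1.3, but both inputs are invented, so this only illustrates the direction.

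**What to change.** In Section 9.4, and then in the SAP:

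- Compute coverage from administrations. Credit each with 7 + 21 = 28 days, merge overlapping windows, and divide the covered days by follow-up. Coverage then cannot exceed 100%. Four weekly doses still earn 21 + 28 = 49 days, and 5 to 7 cycles a year still give 67.1% to 94.0%. Over 365 days, dosing every 7, 14 or 21 days and four-dose cycles started every 42 or 43 days all give 100%. One dose every 60 days gives (6 × 28 + 5)/365 = 47.4%.
- Define continuous and intermittent use by the largest gap between consecutive administrations, keeping the protocol's 120-day limit. A dose every 60 days would then be continuous by gap and infrequent by MPR, so state which label takes precedence.
- Where cycles are still described, use at most 21 days and more than 21 days throughout, and reconcile the four-dose wording with the splitting rule.
- Name cumulative administrations or total duration, both already measured, as the main metric for the duration objective.

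This changes how exposure is classified, not how patients are treated. It needs no new data. The cost is revised wording, slightly more programming, and loss of comparability with cycle-based MPR descriptions.

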9.5 Outcomes

The study outcome of interest is long-term risk of malignancies in patients with MG initiating treatment with efgartigimod and MG patients not treated with efgartigimod, but are on any other therapy for the treatment of MG. Malignancies (examples mentioned in Table 1) will be identified in each of the study databases primarily by using coding algorithms based on International Classification of Disease. Currently Revision 10 is valid, however revisions of the ICD is expected and therefore the version valid at the time of analysis will be used. The algorithms may also consist of relevant procedure codes, and/or results from relevant laboratory tests whenever appropriate and available in the database. All final coding algorithms and detailed code lists will be provided in the SAP.

Table 1. Examples of types of malignancy to be collected, subject to the valid ICD version.

Event of interest	Types of Malignancy	Measurement
Malignancy	
 • Malignant neoplasms of lips, oral cavity and pharynx • Malignant neuroendocrine tumours • Secondary neuroendocrine tumours • Malignant neoplasms of digestive organs • Malignant neoplasms of respiratory and intrathoracic organs • Malignant neoplasms of bone and articular cartilage 	
Incidence rate of events of malignancy by type per patient-years exposed in the efgartigimod treated cohort compared to the reference cohort.
 
Incidence rate ratio and corresponding 95% CIs will be used to compare the malignancy events among the efgartigimod exposed cohort vs. the reference cohort. The calculations will be performed

	
 • Melanoma and other malignant neoplasms of skin • Malignant neoplasms of mesothelial and soft tissue • Malignant neoplasms of breast • Malignant neoplasms of female genital organs • Malignant neoplasms of male genital organs • Malignant neoplasms of urinary tract • Malignant neoplasms of eye, brain and other parts of central nervous system • Malignant neoplasms of thyroid and other endocrine glands • Malignant neoplasms of ill-defined, other secondary and unspecified sites • Malignant neoplasms of lymphoid, hematopoietic and related tissue • Thymic malignancies • In-situ carcinoma 	
separately for each individual database and across all three (3) databases as a meta-analysis according to published methods.

--	---	--

Abbreviation: CI = confidence interval.

Each category of malignancy presented in [Table 1](#) will be assessed individually. If possible, adjudication through review of medical charts will occur for malignancy cases identified through coding algorithms in the claims databases used to conduct the study.

Outcome variables will include:

- Category of malignancy(ies)
- Date of malignancy diagnosis(ses) in a patient’s follow-up period

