Patient accrual into the study will begin following the launch of efgartigimod (differs by country), allowing for a lag between actual exposure dates and appearance of the medication record/procedure in each of the data sources, and will continue for up to 5 years via database refreshes (assumed to be annual). To achieve a desired sample size across all databases, a minimum of approximately 1,358 patients will be included in the efgartigimod cohort and 2,716 matched patients in the reference cohort. Accrual of patients into the study cohorts will be monitored annually. Patients will be followed from study entry to at least 10 years following inclusion in the study. If efgartigimod uptake is slower than expected, patient accrual may need to be extended to reach the required sample size.

² CCI is a method of predicting mortality by classifying or weighting comorbid conditions and has been widely utilized by health researchers to measure burden of disease and case mix. Nineteen (19) conditions are included in the index. Each condition is assigned a weight from 1 to 6, based on severity of the disease and estimated 1-year mortality, and these weights from the comorbidities were added to give a singular numeric score which will act as a way of quantifying current health status.

The study will assess the occurrence of any malignancy according to International Classification of Diseases, Tenth Revision (ICD-10) diagnosis codes, which will be grouped according to the ICD-10 classification system (or to the ICD revision valid at time of analysis). More specifically, the first incidence of and time to any malignancy (incidence rate of events of malignancy per PYs exposed in the efgartigimod treated cohort compared to the reference cohort), as well as incidence rate ratio (IRR) will be estimated.

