13.6 Methods for addressing the potential for outcome misclassification in the claims databases

- Optum: to reduce the potential for false positive malignancy cases based on ICD-10 diagnosis codes in administrative claims database, an algorithm for malignancy case definition will be used that requires at least 2 malignancy diagnoses (within the same site) that are separated by ≥ 30 days.
- SNDS: the SNDS has becoming largely recognised by the French authorities as a powerful tool of pharmacoepidemiology and some guidance and algorithm have been published for the community and one in particular for cancer([Méthode | L'Assurance Maladie \(ameli.fr\)](#)).

14 Quality control

The SOP and work instructions of the sponsor's designated CRO will be used to guide the conduct of the study. These procedures include internal quality audits of the data, consistency of collected data, validation of coding, rules for secure and confidential data storage, methods to maintain and archive project documents, quality control procedures for programming, standards for writing analysis plans, and requirements for senior scientific review. Written programming will be reviewed independently. All key study documents, such as the SAP and study reports, will undergo quality control and senior scientific review.

The study will be executed in line with all applicable regulations and guidelines, such as the Guide on Methodological Standards in Pharmacoepidemiology, the European Network of Centres for Pharmacoepidemiology and Pharmacovigilance (ENCePP) Checklist for Study Protocols, and the International Society of Pharmacoepidemiology (ISPE) Guidelines for Good Pharmacoepidemiology Practices, as well as the data vendor's quality management system.

The SOP and work instructions of the MAH will be used to oversee the execution and conduct of the study by the CRO. These procedures include pre-qualification and in-process quality audits of the CRO's quality management software (QMS) and contracted services. Additionally, the Vendor Relationship Manual will be put in place and will include:

- Performance metrics
- Routine oversight activities
- CRO Governance meetings

The Vendor has SOPs in place which address the extent of source data verification, validation of endpoints, storage of records and archiving of the statistical programming performed to generate the results. These SOPs will be followed in this study.

15 Limitations of the research methods

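### Table 1 pools melanoma with all other skin cancers, and the overall malignancy IRR is planned only with non-melanoma skin cancer included

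*Protocol*

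**What the plan says.** Table 1 in Protocol Section 9.5 gives skin a single row, "Melanoma and other malignant neoplasms of skin". The text below the table says that each category "will be assessed individually". The note to the primary objective in Section 8 sets the by-type grouping: thymic against non-thymic, and "non-thymic will be further categorized into solid tumours by organ and hematopoietic/lymphoid and related" tissue. No level below the organ is named.

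Section 9.1 defines the overall outcome as any malignancy by ICD-10 code and refers to "the first incidence of and time to any malignancy". No section takes NMSC out of that outcome. The list of sensitivity analyses in Section 13.4 is long but contains none without NMSC.

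The case rules differ by source. For Optum, Section 13.6 says that "an algorithm for malignancy case definition will be used that requires at least 2 malignancy diagnoses (within the same site" and at least 30 days apart. For SNDS it points to a published cancer algorithm. It states no rule for CPRD.

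Two statements leave room. The table is titled "Examples of types of malignancy to be collected, subject to the valid ICD version", and Section 9.5 adds that "All final coding algorithms and detailed code lists will be provided in the SAP".

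**The concern.** NMSC and melanoma are different outcomes for a malignancy safety study, and a pooled row can hide an effect on one behind the other. In the overall IRR, an NMSC component that does not respond to treatment pulls a real effect on other cancers towards 1. An NMSC component that is found more often in one cohort pushes the overall IRR away from 1 with no effect on any other cancer.

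A lesion coded once would fail the two-code rule in Optum and might qualify elsewhere. The mix of cancers behind each database's IRR could therefore differ, which adds heterogeneity to a meta-analysis already sized for I² = 0.5.

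Unequal detection is an inference. Section 9.4 says "Majority of patients receive 5-7 cycles per year" with four administrations per cycle, which is 20 to 28 contacts a year (5 × 4 to 7 × 4). The protocol does not say that these visits lead to more skin lesions being found.

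**Working it through.** **Inputs from the protocol (Sections 9.1 and 11, Tables 3 and 4).** Background rate λ = 42.0 per 1,000 PY; follow-up t = 6 years; two reference patients per efgartigimod patient; two-sided 5% test; rate ratio (RR) 1.3. There are 1,358 efgartigimod patients, which the heterogeneity factor of 2 reduces to an effective n = 679.

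**Assumptions not in the protocol.** NMSC share s of background events, 10% to 50%; NMSC detection factor 1.5; for the melanoma example, melanoma is 5% to 20% of the skin row with RR 2.0.

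**Reproducing the plan's power.** Power = Φ( ln RR / √[1/(n·t·λ·RR) + 1/(2·n·t·λ)] − 1.96 ).

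- n·t·λ = 679 × 6 × 0.042 = 171.1.
- Variance = 1/222.4 + 1/342.2 = 0.00742; standard error 0.0861.
- ln 1.3 = 0.2624, and 0.2624/0.0861 = 3.046; Φ(3.046 − 1.96) = 86.13%, the Table 4 figure.

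The Table 4 rows for 42.0 and 60.0 match to two decimals, and the 73.6 rows agree within 0.4 points.

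**Dilution.** NMSC has RR 1.0 and all other cancers RR 1.3. With NMSC kept in, overall RR = 1.3(1 − s) + s at rate λ. With NMSC taken out, RR = 1.3 at rate λ(1 − s).

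| NMSC share s | Overall RR, NMSC in | Power, NMSC in | RR, NMSC out | Power, NMSC out |
|---|---|---|---|---|
| 10% | 1.27 | 79% | 1.3 | 82% |
| 20% | 1.24 | 69% | 1.3 | 78% |
| 30% | 1.21 | 58% | 1.3 | 72% |
| 40% | 1.18 | 46% | 1.3 | 66% |
| 50% | 1.15 | 35% | 1.3 | 58% |

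Check at s = 30%, NMSC in: ln 1.21 = 0.1906, standard error 0.0880, Φ(2.165 − 1.96) = 58%. NMSC out: n·t·λ(1 − s) = 119.8, standard error 0.1029, Φ(2.549 − 1.96) = 72%.

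**False signal.** No effect on any other cancer, NMSC found 1.5 times as often: overall RR = 1 + 0.5s. For s = 10/20/30/40/50% this is 1.05/1.10/1.15/1.20/1.25, nominally significant about 8/18/35/54/73% of the time by the same formula.

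**Melanoma inside the pooled row.** If melanoma is a share m of the skin row with RR 2.0 and the rest has RR 1.0, the row shows 1 + m: 1.05 at m = 5% and 1.20 at m = 20%.

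**Does a first NMSC hide a later cancer?** Section 13.2 models the number of event occurrences. It ends person-time at death, loss to follow-up, end of study or a switch to efgartigimod, and not at a first malignancy. Only the first-event analyses (Sections 9.1 and 13.5) are open to this. At s = 30% over 6 years with independent events:

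- P(another cancer) = 1 − exp(−0.0294 × 6) = 16.2%.
- P(another cancer comes first) = 0.7 × [1 − exp(−0.042 × 6)] = 0.7 × 22.3% = 15.6%.

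**The case against.** The best reply is that this belongs to the SAP. Table 1 gives examples, code lists are deferred, and assessing each category does not forbid a finer split. That stands against the inference that melanoma can never be estimated separately, because an SAP could add the split. It does not answer the point. The protocol itself sets the reporting level and the scope of the overall outcome, and an SAP that simply follows it would pool melanoma and leave NMSC in the headline IRR.

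Second, no passage says that NMSC is frequent, detected more in treated patients or recorded unevenly. This is correct. Only the differing case rules are in the text, and three provisions could soften their effect: procedure codes may enter the algorithms, claims cases may be adjudicated from charts if possible, and one sensitivity analysis drops events in the first 12 months. The last does not address detection that continues throughout treatment.

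Third, skin has its own row, so a skin-driven excess would be visible. This stands in part. The rows would raise suspicion, but they give neither a melanoma estimate nor an adjusted overall IRR free of NMSC.

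Fourth, a reader might infer that NMSC must be left out of the headline outcome. The documents do not support that. The objective is malignancies overall and by type, and exclusion could hide a real skin signal. If NMSC shared the RR of 1.3, keeping it would retain 86% power against 82% to 58% without it.

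Finally, a reader might infer that a first NMSC pre-empts a later serious cancer in the primary analysis. Section 13.2 does not stop at a first malignancy, so this fails there. In the first-event analyses the loss is small.

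**Conclusion.** The point holds as a cheap improvement to the outcome definition. As the protocol is written, melanoma has no estimate of its own, and the overall IRR is planned only with NMSC included, under case rules that differ by database. If NMSC is 10% to 50% of events and unaffected, a true IRR of 1.3 on other cancers is reported as 1.27 to 1.15, and power falls from 86% to between 79% and 35%. A 1.5-fold NMSC detection difference alone would produce 1.05 to 1.25.

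Both the share and the detection factor are assumptions, so these figures show what could happen and do not demonstrate harm. The protocol also does not say whether its rates of 42.0 and 73.6 per 1,000 PY include NMSC. The sample size calculation itself is not in error.

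**What to change.** Split the skin row of Table 1 into melanoma and non-melanoma skin cancer, and assess each separately. Pre-specify the overall malignancy IRR both including and excluding NMSC, in each database and in the meta-analysis, and state before data are seen which is the headline. Say whether the background rates in Section 11 include NMSC, so that the stated power can be read against the chosen version.

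The cost is table wording, a code-list split and one additional IRR. If the 42.0 rate includes NMSC, the version without it has fewer events, and its power at RR 1.3 is 82% to 58% over the assumed range instead of the stated 86.13%.
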